Sample Size: The study will include 30 subjects treated with rituximab and 30 subjects treated with placebo.

Data Analyses: The primary efficacy analysis of change in 6MWD from baseline to 24 weeks will be performed on the intention-to-treat (ITT) population, and will be tested using a repeated measures random effects model to model change from baseline in 6MWD as the primary outcome and treatment as the primary predictor, controlling for visit day, limitations by musculoskeletal disease, baseline levels of 6MWD, and a treatment by visit day interaction. A random slope and intercept will be fit for each subject. An unstructured covariance matrix will be assumed for the random effects. Additional covariates will be considered for this model as part of secondary analysis.

[figure not shown]
Secondary analyses will include repeating the primary analysis in the per protocol population, subgroup analyses of the primary outcome, safety analyses, exploratory analyses of the secondary endpoints, and exploratory analyses of the mechanistic endpoints.

Lay Summary:

Sixty eligible adults between the ages of 18 and 75 who have been diagnosed with SSc-PAH within the past 5 years and meet all entry criteria will be enrolled in this study. Participants will receive 2 infusions (1000 mg) of either rituximab or placebo 14 days apart.

This study will compare patients treated with rituximab to those on placebo for change in six minute walk distance (6MWD). The secondary objectives of this study are to compare treatment groups for other measures of clinical disease progression and to determine whether the effects on clinical disease progression are paralleled by changes in selected biomarkers. Additionally, the safety and tolerability of rituximab for the treatment of SSc-PAH in patients receiving stable background medical treatment with prostanoid, endothelin receptor antagonist, PDE-5 inhibitor, and/or guanylate cyclase stimulators therapy will be assessed.

FLOW DIAGRAM OF PROTOCOL

ABBREVIATIONS

6MWD	6-Minute Walk Distance
6MWT	6-Minute Walk Test
ACE	Autoimmunity Centers of Excellence
ADCC	Antibody-dependent Cellular Cytotoxicity
ADCT	Autoimmune Diseases Clinical Trials
AE	Adverse event
AECA	Anti-Endothelial Cell Antibody
ALP	Alkaline Phosphatase
ALT	Alanine Aminotransferase
ANAs	Serum Antinuclear Antibodies
ANCOVA	Analysis of Covariance
Anti-B23	Antibody to the B23 antigen
Anti-CENP-B	Antibody to the CENP-B (centromere) antigen

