3.1.1 Stratification, Randomization, and Masking

Subjects will be randomized in a 1:1 ratio to receive 2 infusions 14 days apart of either rituximab 1000 mg (treatment arm) or placebo (control arm). The automated randomization system will implement an adaptive randomization procedure to maintain balance between treatment groups overall, by study site, with respect to disease severity as measured by PVR at baseline, and with respect to time since diagnosis of SSc-PAH.

To maintain study blind, the appearance of the packaging and solutions used to administer study drug/placebo will be identical in both study arms.

All clinical and immunology laboratory staff will be masked to the treatment assignments until the completion of the study. In addition, immunology laboratory staff will not have access to any clinical results and clinical staff members, including the investigators, will not have access to any immunology lab results until completion of the study. B cell recovery status and the need for quarterly monitoring visits as defined in Section 6.5.4.12, *Visit 16 [Week 48]* will be communicated to clinical staff upon completion of Visit 16 or Early Endpoint visit. If B cells have not recovered by two years after treatment initiation, B cell levels will be provided to the clinical staff.

Individual treatment assignments will not be unmasked until all subjects have completed the study. In the event a treatment assignment needs to be unmasked for safety reasons, the site PI will notify the SACCC, who will consult with the DAIT medical monitor. The DAIT medical monitor will review the circumstances and grant approval as indicated. In the event of a true medical emergency necessitating immediate unmasking during off-hours, the site pharmacist will confer with the study PI or designee prior to release of the treatment assignment to emergency treating personnel.

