- ²¹ TB testing (PPD or QuantiFERON®-TB Gold In-Tube Test [QFT-G_IT]): unless performed within 30 days prior to screening and documented as negative in the subject's records or unless subject is known to have a positive test and has documentation of appropriate therapy.
- ²² If the Screening physical exam, oxygen saturation, and chemistry panel are performed within 7 days of Day 0, they do not need to be repeated during the Randomization/Baseline or Day 0 visits unless clinically indicated.
- ²³ Only infectious events ≥ NCI-CTCAE grade 3 will be reported.
- ²⁴ Required only if the unscheduled visit is due to an increase in SSc-PAH disease activity; see Section 6.5.8, *Unscheduled Visit* for further details.
- ²⁵ Hemoglobin, platelets, lymphocytes, neutrophils, and bands results from a hematology specimen drawn within 24 hours of the infusion must be reviewed prior to initiating the study drug infusion (see Section 5.3.6, *Criteria for Withholding Rituximab Infusion*).
- ²⁶ A member of the research staff will obtain verbal consent to conduct an assessment of vital status and treatment satisfaction approximately two years post randomization for each subject. If the subject cannot be reached, a review of public records or health registries should be completed.

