The 6MWD has been the most utilized endpoint in PAH trials, and a 33m improvement from baseline is considered clinically significant [160]. For sample size calculations, we assume a change from baseline of 0m for the placebo arm and 33m for the rituximab arm. An effect size of this magnitude is attainable in a 24 week period, and has been seen in as little as 12 weeks in studies using vasodilators. Assuming a standard deviation of 58m (a best guess based on prior studies) and a 20% drop out rate, ASC01 would be powered at 50% to detect a treatment group difference of 33m for this phase II study. If a significant result is found for this primary efficacy endpoint and no safety signals emerge, this study could provide a definitive conclusion about this treatment. In order to achieve 80% power, the true difference between treatment groups would have to be at least 50m. While other studies evaluating other drugs have seen this magnitude of difference in similar timeframes, we have no data on rituximab to suggest the true difference is at least 50m. Furthermore, rituximab would be interesting as a therapy option if the effect size is as small as 33m.

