7.2.2. Primary Analysis of the Primary Endpoint

The primary efficacy analysis for this study is designed to test the scientific hypothesis that rituximab has a beneficial clinical impact on SSc-PAH as measured by improvement or stabilization in 6MWD between baseline to 24 weeks in patients treated with standard of care plus rituximab than in patients treated with standard of care plus placebo. Operationally for this study, this scientific hypothesis will be examined by formally testing the following statistical hypothesis:

H_0 : The mean change in 6MWD between baseline and 24 weeks does not differ between individuals treated with rituximab and those treated with placebo
($\bar{\delta}_{\text{rituximab}} = \bar{\delta}_{\text{placebo}}$ where $\bar{\delta}_x = \text{mean 6MWD at 24 weeks} - \text{mean 6MWD at baseline}$)

versus

H_A : The mean change in 6MWD between baseline and 24 weeks is more beneficial in those individuals treated with rituximab than in those treated with placebo
($\bar{\delta}_{\text{rituximab}} < \bar{\delta}_{\text{placebo}}$ where $\bar{\delta}_x = \text{mean 6MWD at 24 weeks} - \text{mean 6MWD at baseline}$)

While this hypothesis is inherently one-sided, a two-sided test at $\alpha=0.05$ will be used to evaluate the treatment effect at 24 weeks. This primary hypothesis will be tested using a repeated measures random effect model to model the distance walked as a function of treatment, visit week and a treatment by visit week interaction. Additionally, a quadratic term for visit week will be included in the model. A random slope and intercept will be fit for each subject using a separate unstructured covariance matrix for each treatment group. The model will include only 6MWD data up to Week 24. All available data up to Week 24 will be used for subjects who terminate early from the study. All unscheduled visits that occur prior to Week 24 will also be included in the analysis.

Model estimates and standard errors of the distance walked and change from baseline in distance walked will be presented at baseline and Week 24, along with the differences between arms. An appropriate contrast will be used to test the difference (baseline to Week 24) between treatment arms.

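### The primary model takes in every unscheduled walk before Week 24, although such walks are required only when disease worsens, so the Week 24 contrast can be biased if flare rates differ between arms

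*SAP*

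**What the plan says.** SAP 7.2.2 restricts the primary model to 6MWD data up to Week 24 and then adds: "All unscheduled visits that occur prior to Week 24 will also be included in the analysis". SAP 7.1.2 states the general rule that data are analysed whatever the time of assessment. The scheduled walks in the window are Screening and Weeks 4, 12 and 24 (SAP 7.2.1).

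Protocol Table 6.1 marks the walk at an unscheduled visit with footnote 24: "Required only if the unscheduled visit is due to an increase in SSc-PAH disease activity". Protocol 6.5.8 agrees: the walk is among the additional evaluations for visits caused by increased SSc-PAH activity, and at any other unscheduled visit further evaluations are at the investigator's discretion.

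After a fall of more than 20% from Screening the walk is repeated within 7 days (Protocol 6.5.8 applies this to unscheduled visits too), and SAP 7.2.1 uses the better of the two values.

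None of the six items in SAP 7.2.3 drops the unscheduled walks. Item 2 concerns repeats, and item 4 concerns missing data and is optional. Protocol 8.3.2.1 does not mention unscheduled walks, Protocol 8.5.5 adds only the walk of subjects who withdraw before Week 24, and SAP Section 11 lists five changes to the primary model without this one.

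**The concern.** A likelihood-based mixed model tolerates extra visits whose timing depends on walks already recorded. Here the trigger is how the subject is at that moment, which the model has not yet seen. Stable or improving subjects have no required counterpart. Sampling therefore depends on the current outcome.

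SAP 7.2.2 states a quadratic week term but no treatment-by-quadratic term. As written, the Week 24 contrast is 24 times the treatment-by-week coefficient, so a low walk late in the window acts directly on it. If one arm has more transient flares, its slope is pulled down and the other arm is favoured. Unequal worsening is what the trial hopes to see: if rituximab slows progression, placebo subjects flare more and the estimated benefit is inflated.

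**Working it through.** **1. The plan's own figure.** Inputs from Protocol 8.1: "we assume a change from baseline of 0m for the placebo arm and 33m for the rituximab arm"; "Assuming a standard deviation of 58m (a best guess based on prior studies) and a 20% drop out rate". From the synopsis: "The study will include 30 subjects treated with rituximab and 30 subjects treated with placebo". From SAP 7.2.2: two-sided α = 0.05.

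- Completers per arm: 30 × 0.8 = 24.
- SE of the difference: 58 × √(2/24) = 16.74 m.
- Power: Φ(33/16.74 − 1.96) = Φ(0.011) = 50.4%.

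This reproduces the statement "ASC01 would be powered at 50% to detect a treatment group difference of 33m for this phase II study". A noncentral t calculation gives 48.8%.

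**2. Shift caused by unscheduled walks.** No closed formula fits, so the SAP 7.2.2 model was simulated: treatment, week, treatment × week, common week², and random intercept and slope with a separate unstructured covariance per arm. Walks were at Weeks 0, 4, 12 and 24, with 20% of Week 24 missing and the SD of change set to 58 m. Each simulated trial was fitted with and without one possible unscheduled walk per subject in Weeks 5 to 23. Assumptions not in the documents: baseline mean 350 m, between-subject SD 90 m, residual SD 25 m, and all flare rates and depths.

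| Scenario (placebo v rituximab) | Shift in contrast |
|---|---|
| Transient 60 m dip, 20% v 20% | 0.0 to +0.4 m |
| Walk on a bad day only, 30% v 10% | +1.3 m |
| Transient 60 m dip, 30% v 10% | +3.7 m (true difference 0); +3.9 m (true difference 33 m) |
| Same at true difference 0, with better-of-two | +2.8 m |
| Transient 100 m dip, 30% v 10% | +6.3 m |
| Same, with better-of-two | +3.2 m |
| Transient 60 m dip, 50% v 0% | +8.8 m |
| Lasting decline of more than 30 m | 0.0 m (true difference 0); +0.7 m (true difference 33 m) |

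These are large-sample fits with 3,000 or 15,000 per arm. A separate fit with 20,000 per arm gave about +6 m for a transient 60 m dip at 30% v 10%, before the better-of-two rule. The figure therefore depends on the set-up, including how late in the window the walk falls.

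**3. Trial-size error rate.** In 600 trials of 30 per arm with a true Week 24 difference of 0, the scheduled-only fit rejected in 6.2%. With unscheduled walks the rate was 5.7% (20% v 20%, 60 m dip), 6.5% (30% v 10%, 60 m) and 8.2% (30% v 10%, 100 m). Monte Carlo error is about 1 point. The mean model SE was about 16 m.

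**4. What a few metres do at 50% power.** Hold the SE at 16.74 m and let the true effect be 33 m.

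- Shift of 3.9 m: Φ(36.9/16.74 − 1.96) = Φ(0.244) = 60%.
- Shift of 6.3 m (estimated at a true difference of 0 and carried over by assumption): Φ(39.3/16.74 − 1.96) = Φ(0.388) = 65%.

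**The case against.** **The bias is not certain.** A reader might infer that the contrast is biased as a matter of course. The documents do not support that. With equal flare rates the shift is about zero. With lasting decline the subject's own random slope absorbs nearly all of it. Bias needs both an imbalance between arms and dips that a straight line does not explain. This stands.

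**The repeat rule already helps.** At the assumed 350 m baseline it acts on falls of more than 70 m. It roughly halves the shift for a 100 m dip but does less for a 60 m dip. This stands as partial mitigation.

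**Dropping the walks can do harm.** Suppose 30% of placebo and 10% of rituximab subjects have a lasting 80 m decline in Weeks 13 to 22. The true contrast is then about 0.20 × 80 = 16 m. If 80% of those who decline miss Week 24 and have no Early Endpoint Visit walk, the fit with unscheduled walks gives 17.5 m and the fit without gives 4.4 m. The risk is real, but it arises only when the Early Endpoint Visit walk is absent. With that walk kept, scheduled-only errors were about 1 to 2 m, against about 4 to 6 m under the SAP rule.

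**The Early Endpoint Visit is also triggered by worsening** (Protocol 3.3.2.1 and 6.5.6). That is true, so keeping it does not remove all outcome-dependent sampling. It differs in that it stands in for the walks such a subject will not go on to provide, and Protocol 8.5.5 already counts it.

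**The rule is pre-specified.** It is, in SAP 7.1.2 and 7.2.2, and using all available data is defensible when 20% dropout is expected. What is missing is any planned analysis that shows how much the result depends on the rule.

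**Conclusion.** The concern holds in conditional form. Required unscheduled walks are tied to worsening, all of them enter the primary model, and no planned analysis removes them. The Week 24 contrast can therefore be biased in favour of the arm with fewer flares. Under the assumptions above, the plausible shift at 30% v 10% is about 1 to 6 m, or 0.1 to 0.4 of a standard error. The 50% v 0% case, at about 9 m, is extreme. The stated design power does not change.

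Two stronger readings should be resisted. One is that the type I error is materially inflated. If rituximab changes neither flares nor walking, flare rates are equal in expectation and no inflation was seen. The rise to 8.2% needs deep transient flares that differ by arm with no Week 24 difference. The other is that infections on rituximab would generate low walks and overstate harm. An infection visit does not by itself require a walk, so the documents do not support that route.

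The point matters mainly for a borderline result. With 50% power at 33 m, the expected estimate sits almost on the significance threshold.

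**What to change.** Before unmasking, amend the SAP as follows.

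- **7.2.2:** fit the primary model to the Screening and Week 4, 12 and 24 walks, with their protocol repeats, plus the Early Endpoint Visit walk. That last walk must be retained.
- **7.2.3:** add the fit that includes unscheduled walks as a sensitivity analysis. If the primary rule is left as it is, the minimum is to pre-specify here a fit without unscheduled walks.
- **Reporting:** give the number of unscheduled walks by arm, and show both fits side by side.
- **Section 11:** list the rule on unscheduled walks, whichever way it is settled.

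Unscheduled walks still count towards clinical worsening in SAP 7.3.3.

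The cost is SAP wording and a few walks leaving the primary model. The downside is that subjects who worsen and then die or are lost without an Early Endpoint Visit walk lose their last evidence of decline, which is why both fits should be reported.

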7.2.3. Sensitivity Analyses of the Primary Endpoint

The following sensitivity analyses will be performed:

1. Primary analyses performed on both PP populations.
2. If a subject's 6MWD decreased from Screening by more than 20% and a repeat 6MWD was performed, then models will be developed using both 6MWD values and also using just the second, confirmatory, value in the model.
3. Changes in background PAH medications prior to Week 24 (yes/no) will be added as a covariate to the model.
4. Missing data will not be imputed for the primary endpoint. However, sensitivity analyses may be performed to assess the robustness of the conclusions under different

assumptions. For example, missing data due to death of a subject prior to Week 24 would be handled differently than missing data due to a missed visit. A joint longitudinal/survival model to evaluate trends in clinical assessments under different assumptions about the underlying missing data mechanism may be considered, if appropriate.

5. Demographic and baseline characteristics that differ meaningfully between the two treatment groups (with or without a p-value <0.05) may be included in a covariate-adjusted model, as appropriate.
6. Time-varying covariates, like oxygen use during SMWD, may be added as appropriate.

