11. CHANGES TO THE ANALYSES PLANNED IN THE PROTOCOL

[figure not shown]
1. Section 7.2.2: Primary endpoint:
 - a. Actual values rather than change from baseline in 6MWD will be used in the model.
 - b. Remove baseline measures of 6MWD as covariate
 - c. Use visit week rather than visit day
 - d. Addition of quadratic term for visit week
 - e. Remove limitations from musculoskeletal disease as a covariate. The number of “yes” occurrences is too sparse to inform the analysis.
2. Section 7.3.3: Clinical worsening: Protocol says “worsening of 6MWD by > 20% and a decrease in functional class” vs. corrected “worsening of 6MWD by > 20% and an increase in functional class”
3. Section 7.3.4: Analyses changed from using a logistic regression model to analyzing time to first change or addition of PAH medications.

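### SAP 7.2.3 item 3 enters PAH-drug change as a subject-level main effect, which barely moves the baseline-to-Week-24 contrast, so a robust-looking result would say little

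*SAP*

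**What the plan says.** SAP 7.2.2 sets out to "model the distance walked as a function of treatment, visit week and a treatment by visit week interaction", with a quadratic week term and a random intercept and slope whose covariance differs by arm. The arm difference in change from baseline to Week 24 is then tested by a contrast: "a two-sided test at $\alpha=0.05$ will be used to evaluate the treatment effect at 24 weeks". SAP Section 11 records the change of outcome from the protocol: "Actual values rather than change from baseline in 6MWD will be used in the model".

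SAP 7.2.3 lists the sensitivity analyses. Item 3 is a commitment: "Changes in background PAH medications prior to Week 24 (yes/no) will be added as a covariate to the model". That is one yes/no value per subject, and no interaction with week is named. Item 5 is optional: baseline characteristics that differ meaningfully between arms "may be included in a covariate-adjusted model, as appropriate", with the functional form left open. Item 6 separately allows time-varying covariates, also optionally.

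**The concern.** Item 3 is the only analysis in 7.2.3 aimed directly at changes in background PAH drugs. Protocol 1.5.1 gives the confounding effect of such changes as its reason for requiring stable therapy. A reader will take an unchanged estimate under item 3 as evidence that drug changes do not explain the 6MWD result. If the added term can hardly reach the tested contrast, the estimate stays nearly the same whether or not drug changes altered the trajectory, and that reassurance is empty. An item 5 adjustment for a chance baseline imbalance would have the same weakness if fitted as a main effect.

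**Working it through.** **1. The plan's own figure.** Protocol 8.1 states: "we assume a change from baseline of 0m for the placebo arm and 33m for the rituximab arm"; "Assuming a standard deviation of 58m (a best guess based on prior studies) and a 20% drop out rate"; and "ASC01 would be powered at 50% to detect a treatment group difference of 33m". With 30 × 0.8 = 24 per arm, the standard error is 58 × √(2/24) = 16.7 m and 33/16.7 = 1.97. Power is Φ(1.97 − 1.96) ≈ 50.4% (48.8% with the noncentral t). The stated 50% reproduces, and it sets the scale: a shift matters when it is an appreciable part of 15 to 19 m.

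**2. Algebra.** Let T be treatment, t week and x the subject-level covariate. Item 3 as written gives

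E(Y) = β0 + β1·T + β2·t + β3·t² + β4·T·t + γ·x.

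The expected change from week 0 to week 24 is 24β2 + 576β3 + 24β4·T. The term γ·x cancels, and the tested contrast is 24β4 with or without x.

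With complete walks at common weeks the estimates also coincide. Each subject's data reduce to an intercept and a slope. Within each arm the estimating equations for mean intercept and mean slope force both sets of residuals to sum to zero, whatever that arm's covariance. The slope estimate is therefore the arm mean of the subject slopes, and x does not enter. With x·t added, the expected change gains 24δ·x, and the covariate can then act on the contrast.

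**3. Simulation with incomplete data.** From the documents: 30 per arm, walks at weeks 0, 4, 12 and 24, and the SAP 7.2.2 model. Assumed, because the documents do not give them: baseline SD 95 m, residual SD 30 m, Week 24 slope SD 40 m, intercept-slope correlation −0.2. The implied SD of change is √(40² + 2 × 30²) = 58.3 m, which agrees with the protocol. Each cell gives generalised least squares with known covariance (2,000 trials), then REML with arm-specific covariance (60 trials).

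- A: complete, on schedule; covariate present in 35% of one arm and 10% of the other; −60 m on level and on Week 24 change.
- B: as A, with ±7-day visit windows.
- C: as A, but subjects with a PAH change leave at weeks 6 to 22.
- D: as C, 40% and 5%, effects −120 m.
- E: baseline covariate, 60% and 30%, effects −60 m, 20% dropout.

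| | Main effect: mean absolute shift, m | Largest shift, m | 5% decision changed | Plus covariate × week: mean shift, m | 5% decision changed (least squares) |
|---|---|---|---|---|---|
| A | 0.00 / 0.00 | 0.00 / 0.00 | 0/2000, 0/60 | −15.0 / −16.7 | 799/2000 (40%) |
| B | 0.01 / 0.05 | 0.09 / 0.27 | 0/2000, 0/60 | −15.1 / −15.0 | 794/2000 (40%) |
| C | 0.65 / 0.95 | 3.1 / 4.4 | 26/2000 (1.3%), 1/60 | −9.1 / −10.9 | 428/2000 (21%) |
| D | 1.7 / 2.7 | 5.8 / 9.6 | 48/2000 (2.4%), 1/60 | −25.6 / −33.6 | 1132/2000 (57%) |
| E | 0.45 / 1.0 | 2.8 / 3.3 | 15/2000 (0.75%), 1/60 | −18.1 / −17.6 | 846/2000 (42%) |

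The standard error was about 14.5 to 15.6 m in A and B and about 16 to 19 m in C to E. As a check, the interaction shifts match the built-in imbalance: 60 × (0.35 − 0.10) = 15 m in A and 60 × (0.60 − 0.30) = 18 m in E.

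**4. A baseline imbalance (item 5).** Take a true effect of 33 m and a factor in 40% of rituximab and 20% of placebo subjects that lowers the Week 24 change by 60 m. The imbalance contributes −60 × (0.40 − 0.20) = −12 m. Over 1,000 trials with complete walks the mean estimate was 21.3 m unadjusted, 21.3 m with the main effect and 33.1 m with covariate × week. The last verdict differed from the unadjusted one in 30% of trials.

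**The case against.** The best reply is that this trial's data will not be balanced. SAP 7.2.2 keeps early terminators and unscheduled visits, and Protocol 3.1 and 6.5.6 tie new PAH therapy for worsening disease to an early endpoint visit. A reader might infer from the algebra that the estimate cannot move at all. That does not stand: the largest simulated shift was 9.6 m, in the most extreme setting, and a few decisions changed. What does stand is that the typical movement is small against the standard error.

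It can also be said that the SAP never excludes a week interaction. For item 5 this is fair, since that item is optional and its form is open. For item 3 the main effect is the natural reading. The SAP names interactions where it wants them: with week in 7.3.1, and in 7.3.2 for this same kind of covariate, with treatment only.

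A reader might go further and say that the change of outcome removed a working adjustment without notice. The documents do not support this. Section 11 lists both the move to actual values and the removal of the baseline covariate, and Protocol 8.3.2.1 names no PAH-change covariate and leaves sensitivity analyses to the SAP. Nor would the protocol's model have adjusted fully: with a 12 m imbalance, a main effect in a change-from-baseline model moved the mean estimate only from 20.6 to 24.8 m.

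Finally, PAH-drug change arises after randomisation. A reader might call it a confounder whose bias the interaction removes. It may instead be a mediator, so the shifts in C and D show what the term can detect; they are not a correction towards the truth.

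Item 6 is not subject to the problem but is optional. The per-protocol rerun in item 1 excludes subjects rather than modelling drug change, so it answers a different question.

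**Conclusion.** The point holds for item 3 as written, and for item 5 if its covariates are entered as main effects. With complete, on-schedule walks the contrast is exactly unchanged; this is algebra and needs no numerical assumption. Under visit-window variation alone the shift is negligible. With early exits it averages 0.45 to 2.7 m against a standard error of about 16 to 19 m, and the decision changes in about 0.75% to 2.4% of trials. These sizes depend on the assumed variances, covariate frequencies and effects, none of which the documents give. An unchanged result would be weak evidence that PAH-drug changes, or a baseline imbalance, left the 6MWD trajectory alone. The primary estimate, test and error rate are untouched, so this is a change that should be made to a supportive analysis and not a fault in the main one.

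**What to change.** In SAP 7.2.3 item 3, enter PAH-drug change plus PAH-drug change × visit week. Report the arm-specific changes to Week 24 at the pooled covariate mean; without a three-way term, the arm difference is the same at any covariate value. Label the result descriptive, because the variable is post-randomisation and may be a mediator.

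A per-walk indicator (0 before the change, 1 from it on) may be added, since SAP 7.3.4 already collects the date of the first change, but it should not stand alone. Protocol 6.5.6 places the Early Endpoint Visit before the drug change, and Protocol 3.3.2.1 describes only B-cell and infection monitoring afterwards, so few walks of subjects with progressive PAH would be coded 1. In a simulation with early exits it moved the estimate by 2.8 m, against 9.8 m for covariate × week.

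In item 5, state that any baseline covariate adjusted for is entered as covariate plus covariate × visit week, again evaluated at the pooled mean.

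The cost is SAP wording, one more fixed-effect parameter per covariate, and a standard error about 0.3 to 0.4 m larger (for example 14.8 to 15.1 m in step 4).
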